Objective(s):	
To investigate the efficacy in terms of 6 month progression free survival (PFS6) and objective response rate (ORR) of afatinib, in patients with advanced/metastatic urothelial tract carcinoma who have progressed despite prior platinum based chemotherapy. Two cohorts will be analysed separately: Cohort A will investigate patients with ERBB2 amplification and ERBB2 or ERBB3 mutations; Cohort B will investigate patients with EGFR amplification.
 
Other measures of efficacy include progression free survival (PFS), overall survival (OS), disease control rate (DCR), duration of objective response (DOR), and tumour shrinkage.
 
Safety will be assessed throughout the trial by AEs according to NCI CTCAE v. 4.03.
		
Methodology:	Un-controlled, open-label phase II trial using a two stage design for Cohort A. Cohort B will be hypothesis generating. Patients will be assigned to Cohort A (ERBB2/3 genetic alterations) or Cohort B (EGFR amplification) based on screening biomarkers. In case of competing recruitment, Cohort A will be accrued first.		

Name of company:		Boehringer Ingelheim	
Name of finished product:		Giotrif, Gilotrif	
Name of active ingredient:		Afatinib (BIBW 2992)	
Protocol date: 17 FEB 2016	Trial number: 1200.261		Revision date: 13 MAR 2017
No. of patients:	Approximately 350 patients will need to be screened to allow for 80 patients who are entered and treated in Cohort A (up to 70 patients) and Cohort B (up to 10 patients) and evaluable for PFS6		
total entered:	Approximately 350 patients to be screened Up to 80 patients to be treated		
each treatment:	Approximately 350 patients to be screened Cohort A: up to 70 patients treated 
 • Stage 1: 25 patients • Stage 2: 45 patients Cohort B: up to 10 patients treated		
Diagnosis :	Patients with histologically confirmed advanced/metastatic urothelial tract carcinoma who progressed despite platinum based therapy, and show mutations in ERBB2 or ERBB3 or amplification in ERBB2 (Cohort A), or EGFR amplification (Cohort B).		
Main criteria for inclusion:	
 • Histologically confirmed urothelial tract carcinoma of the bladder, upper tract or urethra • Locally advanced or metastatic urothelial tract carcinoma not amenable to surgical treatment • Progressed on or after platinum based therapy prior to enrolment and not candidate for another platinum therapy. • Measurable disease per RECIST 1.1 • Archival tissue sample available for biomarker testing and tissue banking 
 ○ Cohort A: ERBB2 or ERBB3-mutation(s) or ERBB2-amplification ○ Cohort B: EGFR amplification • ECOG performance status 0-1 • Adequate bone marrow, hepatic and renal function 		
Test product(s):	Afatinib (Giotrif, Gilotrif) 20 mg, 30 mg, 40 mg afatinib film coated tablets		
dose:	40 mg once daily given continuously; the dose can be reduced in 10 mg decrements down to 20 mg daily in case of intolerable AEs.		

Name of company:		Boehringer Ingelheim	
Name of finished product:		Giotrif, Gilotrif	
Name of active ingredient:		Afatinib (BIBW 2992)	
Protocol date: 17 FEB 2016	Trial number: 1200.261		Revision date: 13 MAR 2017
mode of administration:	Oral, p.o		
Comparator products:	Not applicable		
dose:	Not applicable		
mode of administration:	Not applicable		
Duration of treatment:	Therapy with afatinib will continue until progression of disease as confirmed by imaging according to RECIST 1.1, or patient's withdrawal of consent for continuation of treatment, or other reasons requiring treatment discontinuation (see Section 3.3.4.1). It is anticipated that the average time on treatment will be ≥ 6 months.		
Endpoints	Primary endpoint: Progression free survival rate at 6 months (PFS6) for Cohort A patients. Key secondary endpoint: ORR for Cohort A patients Other secondary endpoints: PFS, OS, DCR, DOR, tumour shrinkage for Cohort A patients. Cohort A and Cohort B will be analyzed separately.		
Safety criteria:	Evaluation of safety and tolerability of afatinib by incidence and severity of adverse events according to NCI Common Terminology Criteria for Adverse Events (CTCAE) version 4.03		
Statistical methods:	Cohort A: Will be evaluated with a two stage design based on PFS6. PFS6 will be calculated as the proportion of patients who are alive and without disease progression at the 24-week tumour assessment. Objective response rate will be calculated as the proportion of patients with confirmed complete response or confirmed partial response. Further, PFS and OS will be evaluated using the Kaplan-Meier estimate. Duration of objective response will be summarized descriptively. All analyses will be descriptive in nature. Cohort B: The analyses will be exploratory and descriptive in nature.		

FLOW CHART

Trial periods	Pre-screening	Screening	Treatment courses							EOT ¹	EoR ²	Follow-up for progression ³	Follow-up for OS ⁴
			1			2		3	4 and onwards				
			1	2	3	1	2	1	1				
Day of period	Any time prior to day -29 ⁶	-28 to -1	1	8 ±2	15 ±2 ⁷	1 ±2	8 ±2 ⁷	1 ±2	1 ±2				
Pre-screening consent	X ⁸												
Tumour sample tissue availability	X ⁹												
Informed consent		X ¹⁰											
Demographics		X											
Medical history		X											
Physical examination		X	X	X		X		X	X	X			
Performance score ¹¹		X	X			X		X	X	X		X	
Vital signs		X	X	X		X		X	X	X			
Height		X											
Weight		X	X	X		X		X	X	X			
Safety laboratory tests ¹²		X	X	X		X		X	X	X			
Pregnancy test (if appl.) ¹³		X								X			
12 lead-ECG ¹⁴		X		X					X	X			
Disease assessment imaging ¹⁵		X								X		X	
Review in-/ex- criteria		X											
Blood and urine for biomarker testing ¹⁶		X							X	X		X	
Blood for PGx			X ¹⁷										
Dose assessment			X			X		X	X				
Dispense trial drug ¹⁸			X			X		X	X				
Afatinib administration						X							
Adverse events ¹⁹		X	X	X	X	X	X	X	X	X	X	X	X
Concomitant therapies		X	X	X	X	X	X	X	X	X	X	X	X
Compliance check						X		X	X	X			
Eligibility for treatment continuation						X		X	X				
Conclusion of treatment										X			
Conclusion of patient participation ²⁰											X	X	X
Survival status													X ₁
Subsequent anti-cancer therapy												X	X

1. EOT = End of treatment – When the decision is taken to permanently discontinue the study medication, the EOT visit must be performed within 7 days after last administration of afatinib. If the decision is taken at a scheduled visit, the EOT visit will be performed instead of the scheduled visit. Examinations performed at this time may need to be renamed for the actual visit conducted
2. EoR = End of residual effect period. Safety follow-up visit not earlier than 30 days (+7 days) after last afatinib administration.
3. Follow-up for progression = Additional follow-up visit. Patients who have not progressed at EOR should have additional limited follow-up visits at scheduled tumour assessment timepoints until progression, consent withdrawal, lost to follow-up or death.
4. Follow-up for OS= Follow-up for overall survival: collection of information on vital status every 90 days. Information could be collected from the patient's notes or by telephone contact. A formal visit is not required
5. All courses are of 4 weeks duration (28 days). Day 1 of a new course should take place on day 29. Patients may continue on treatment for unlimited courses until the criteria for stopping medication are met (see [Section 3.3.4](#)). Two additional visits are performed during course 1 to assess tolerability. From course 3 onwards, only one visit per course is required

6. Pre-screening period can start at any time after signature of pre-screening consent, but please allow at least 4 weeks for assessment of biomarkers and delivery of results.
7. Patient contact to be done 15 days after starting study medication, and one week after starting treatment Course 2, to check for Adverse Events and Concomitant medication. Information could be collected by telephone contact. A formal visit is not required if not needed.
8. Before tumour tissue sample collection for assessment of eligibility into the trial the patient has to give informed consent according to the local regulatory requirements. This consent includes consent to maintain 5x1 mm cores for TMAs of tissue sample when the patient is not eligible, or the tissue block if the patient is eligible.
9. Patient must consent for collection of tumour sample, to (i) perform pre-screening for inclusion into the trial and (ii) archiving of tissue for bridging of companion diagnostics assay if needed.
10. Once the patient was eligible for the trial by pre-screening, before to commence any additional trial procedure the patient has to give informed consent/assent for trial participation according to the local regulatory requirements. At each moment along the trial, the site staff must disclose and discuss any new information that might affect willingness to continue trial participation with the patient and/or legal guardian.
11. Performance score will be assessed according to ECOG
12. Safety lab tests to be performed as described in [Section 5.3.3](#), but should not be repeated if previous tests are older than 48 hours
13. Mandatory for female patients of child bearing potential (post menarchal) within 7 days prior to first treatment and at EOT. To ensure early detection of pregnancy, test might be repeated as necessary during the treatment period depending on the local law
14. ECG is required at screening, at C1V2, and V1 of every third course thereafter (i.e. C4V1, C7V1...) and EOT
15. Tumour assessment by Imaging (CT or MRI) should be performed every 8 weeks (+/- 1 week) calculated from the first treatment day to the end of study treatment. If treatment discontinuation is for other reason than disease progression, further tumour assessments should be obtained as follows: every 8 weeks (+/-1 week) until month 6, and every 12 weeks (+/-2 weeks) from 6 months onwards, until documented progression of disease. Baseline CT/MRI must be performed within 28 days before start of study treatment (if an assessment was performed within this timeframe, patient would not need to repeat this test).
16. Blood and urine for biomarker testing will be collected at screening, then every 4th cycle during treatment, and also at End of Treatment. If a patient has not progressed at End of Treatment then samples should continue to be collected at every 4th follow-up visit and also at the last follow-up visit (as described in [Section 5.5](#)).
17. Pharmacogenetics: one optional blood sample, to be obtained only after signing of PGx consent at any treatment visit.
18. New kit(s) of trial drug must be dispensed at visit1 of each course. If needed (e.g. in case a dose adaptation has to be applied during treatment course), new kit(s) of trial drug might be dispensed outside of the planned visit schedule
19. AE/SAE should be reviewed at every treatment visit, at EOT, EOR and thereafter as described in [section 5.3.6](#).
20. Conclusion of patient participation: should be recorded at the last follow-up visit, when PD/Death occurs, consent withdrawal or death
21. All patients will be followed-up for overall survival at 90 days intervals. For patients who progressed on treatment, the observation period for overall survival starts after the EoR. For patients who have not progressed on treatment, this period starts after the last follow-up for progression visit. The End of the Trial will be achieved as described in [Section 8.6](#).

TABLE OF CONTENTS

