1.1 MEDICAL BACKGROUND

Bladder cancer is the most common cancer of the urinary tract with ~380,000 new cases and ~150,000 deaths per year worldwide ([R13-1113](#)). It is the fifth most prevalent among cancers in men in Western countries and >90% of bladder cancers are transitional cell carcinomas of the urothelium (TCCU), or, to simplify, urothelial carcinomas ([R15-3970](#)). In 2012, there were an estimated 577,403 people living with bladder cancer in the US and the number of new cases of bladder cancer was 20.3 per 100,000 men and women per year with 4.4 deaths per 100,000 men and women per year. These rates are age-adjusted and based on 2008-2012 cases and deaths ([R15-5922](#)). Muscle-invasive bladder cancers (MIBC) account for 33% of all bladder cancers, i.e about 125,400 patients per year are diagnosed with this subtype, and an additional 15-30% (37,620 to 75,240) of patients’ with non muscle-invasive bladder cancers (NMIBC) progress into MIBC. As described by Knolwes et al and Rebouissou et al ([R15-3968](#); [R15-3974](#)) about 20% of patients with urothelial cancer carry ERBB genetic alterations.

Adjuvant treatment consists of neoadjuvantly or adjuvantly applied chemotherapy with DDMVAC, gemcitabine and cisplatin or CMV with or without radiotherapy and surgical cystectomy. Treatment in 1st line metastatic setting is largely confined to chemotherapy utilizing the regimes given in adjuvant setting ([R15-3966](#)). Treatment for patients with platinum refractory locally advanced or metastatic TCCU has not advanced for several decades, and at present no established standard of care nor an approved therapy by FDA or EMA exists and patients are generally entered into clinical trials ([R15-3966](#), [R15-5942](#)). Median PFS published from various trial settings ranges between 2.9 and 4.0 months, median OS between 5.0 to 9.6 months ([R15-3967](#); [R15-3969](#); [R15-3971](#); [R15-3972](#); [R15-3973](#)). Until recently chemotherapeutic agents of randomized trials have not been able to show OS benefit when compared to best supportive care (BSC), and have had the added burden of toxicity. New therapies for this disease, which has a very dismal prognosis, are needed.

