5.3.3 Safety laboratory parameters

Safety lab will be performed locally at each participating site. Following parameters should be evaluated at each timepoint:

Table 5.3.3: 1 Safety laboratory parameters

Category	Parameters
Hematology	Red blood cell count (RBC), haemoglobin, haematocrit, platelet count, white blood cell count (WBC), with differential (neutrophils, lymphocytes, monocytes, eosinophils, basophils)
Coagulation	International Normalized Ratio (INR), activated Partial Thromboplastin Time (aPTT), Fibrinogen.
Chemistry	
Electrolytes	Sodium, potassium, calcium, magnesium, chloride, bicarbonate (HCO ₃)
Liver function tests	alkaline phosphatase, aspartate aminotransferase (AST), alanine aminotransferase (ALT), γ - glutamyltransferase (GGT), total bilirubin
Renal function parameters	Blood urea/blood urea nitrogen (BUN), creatinine; Creatinine clearance (see Appendix 10.2).
Other	glucose, albumin, cholesterol, triglycerides, phosphorus, lactate dehydrogenase (LDH), total protein, uric acid, creatine phosphokinase (CPK); in case of pathological CPK further evaluation (e.g by determination of isoenzymes, troponin assays, ECG exam) should be performed as clinically indicated
Urinalysis	pH, protein, glucose, ketones, blood, leucocytes, nitrite; in case of pathological finding further evaluation should be performed and results documented. Proteinuria per se will only result in treatment interruptions if associated to other renal pathology which would qualify for treatment interruption i.e. CTCAE \geq 3 AE, or decrease in renal clearance to $<$ 45 ml/min GFR
Pregnancy test	β -HCG testing in urine or serum in women of childbearing potential (WOCBP)

The investigator should complete additional evaluations of laboratory tests as clinically indicated.

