6.2.2 Treatment period(s)

Every treatment course is defined as 28 days. All subsequent visit dates should be calculated based on Course 1 Visit 1 date. If a visit is missed there will be no re-scheduling; if a patient should attend the study site between the “missed” and the next scheduled visit, then the missed visit assessments should be performed.

The investigations are outlined in the [Flow Chart](#) and will be performed at the respective visit, but are described in detail in the following sections.

During the first visit of each treatment course, the following procedures will be performed:

- Physical examination: complete medical examination including body weight
- ECOG performance status
- Vital signs
- Safety lab: haematology, biochemistry, coagulation parameters and urine analysis as described in [Section 5.3.3](#).
- Dispense study medication, and dose assessment
- Review of adverse events and concomitant medication

During Course 1, an additional visit will be performed 8 days after the start of treatment (C1V2). The main objective of this visit is to assess the safety profile of trial drug. The exact procedures to be done are described in the study [flowchart](#).

Additionally, a patient contact is to be done 15 days after starting study medication, and one week after starting treatment Course 2, to check for adverse events and concomitant medication. Information for these contacts could be collected by phone. A formal visit is not required if not needed.

Additionally, the following procedures will be done at specific timepoints:

- 12-lead ECG, to be performed at screening, C1V2, C4V1, and every third course thereafter (C7V1, C10V1,...)
- At the end of second treatment cycle, i.e. 8 weeks after the start of study medication and every 8 weeks thereafter, tumour imaging to assess response to treatment must be

performed. In case of objective response, the latter has to be confirmed 4 to 6 weeks after initial OR observation.

- A plasma and an urine sample will be stored for exploratory analyses – for details see [Section 5.5](#).

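### Flow chart footnote 12 inverts its 48-hour condition: read literally, safety labs are withheld when the last results are old, against the visit schedule

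*Protocol*

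**What the plan says.** The Flow Chart row "Safety laboratory tests ¹²" marks labs at screening, Course 1 Visit 1 (C1V1), Course 1 Visit 2 (C1V2), Visit 1 of every later course and end of treatment (EOT). Footnote 12, attached to that row, refers to Section 5.3.3 for the tests and then adds: "but should not be repeated if previous tests are older than 48 hours".

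Three other places bear on the same labs:

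- Protocol Section 5.3.3 introduces the panel with "Following parameters should be evaluated at each timepoint" and contains no exemption based on the age of earlier results.
- Protocol Section 6.2.2 opens its list with "During the first visit of each treatment course, the following procedures will be performed", and the list includes "Safety lab: haematology, biochemistry, coagulation parameters and urine analysis".
- Protocol Section 6.2.2 also fixes the timing: "All subsequent visit dates should be calculated based on Course 1 Visit 1 date".

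Footnote 15 of the same Flow Chart has a comparable exemption for baseline imaging within 28 days of starting treatment: "if an assessment was performed within this timeframe, patient would not need to repeat this test".

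**The concern.** A no-repeat rule normally spares the patient a second draw when a recent result is already in hand. Footnote 12 does the opposite. It applies when the earlier result is more than 48 hours old, which is when a new one is needed, and it says nothing about results obtained the day before. The likely cause is a missing negative before the word for older, or a superfluous one earlier in the clause. Either repair leads to the same rule.

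The footnote sits in the table that sites work from, and the labs it governs feed safety decisions: the hepatic injury alert (Protocol Section 5.3.5.1), dose interruption and reduction for reduced renal function (Protocol Table 4.1.4.1.1: 1), and the laboratory summaries by planned assessment and CTCAE grade transition (Protocol Section 7.3.4; SAP Section 7.8.2). Followed exactly, the footnote would suppress scheduled on-treatment labs. Even with a sensible reading, a site holding screening labs drawn the day before C1V1 is not told that it may skip the repeat, and a monitor has no consistent standard for what counts as a deviation.

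**Working it through.** The plan gives no figure to reproduce here. The check compares the gaps between scheduled labs with the 48-hour limit, and then counts the labs that a literal reading would affect.

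**Inputs.** From the Flow Chart: screening on Day -28 to -1; C1V1 on Day 1; C1V2 on Day 8 ± 2; Visit 1 of later courses ± 2 days; courses of 28 days. From Protocol Section 6.2.2: all visit dates are anchored on C1V1. From SAP Section 6.7: there is no Day 0.

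**Windows.** C1V2 falls on Day 6–10. C2V1 is nominally Day 29, so Day 27–31. C3V1 is nominally Day 57, so Day 55–59.

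**Gaps** (minimum = earliest later visit minus latest earlier visit; maximum = the reverse):

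| Interval | Minimum | Maximum | In hours |
|---|---|---|---|
| C1V1 to C1V2 | 6 − 1 = 5 days | 10 − 1 = 9 days | 120–216 |
| C1V2 to C2V1 | 27 − 10 = 17 days | 31 − 6 = 25 days | 408–600 |
| C2V1 to C3V1, and later Visit 1 to Visit 1 | 55 − 31 = 24 days | 59 − 27 = 32 days | 576–768 |

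The shortest gap is 120 h, against a limit of 48 h. At every fixed on-treatment lab after C1V1, the previous scheduled test is therefore older than 48 hours and the literal condition is met.

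**Labs outside that statement.** The first screening lab has no predecessor in the trial. For C1V1, a screening lab on Day -1 is 1 day old and one on Day -2 is 2 days old. Any of the other 28 − 2 = 26 permitted days gives a gap above 48 h. A Day -2 draw sits at about 48 h and depends on clock time. An EOT lab escapes only if it closely follows another lab.

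**Labs per patient under a literal reading.** Nominal days are C1V2 Day 8, C2V1 Day 29, C3V1 Day 57, C4V1 Day 85, C5V1 Day 113 and C6V1 Day 141. As an assumption for time on treatment I use the range in Protocol Section 1.1, "Median PFS published from various trial settings ranges between 2.9 and 4.0 months", at 30.4 days per month:

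- 2.9 × 30.4 ≈ Day 88: C1V2, C2V1, C3V1 and C4V1, so 4 labs.
- 4.0 × 30.4 ≈ Day 122: C5V1 is added, so 5 labs.
- Six complete courses, 6 × 28 = Day 168: C6V1 is added, so 6 labs. This is close to the synopsis, which anticipates an average of at least 6 months on treatment.

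Any C1V1 or EOT lab drawn more than 48 h after the one before it would come on top.

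**Is it corrected elsewhere?** Section 11 (Amendment 1) lists changes to Flow Chart footnotes 2, 4, 5, 7 and 15, and none to 12. No other section states a 48-hour rule for labs.

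**The case against.** The strongest reply is that nobody would follow the literal text. The first half of footnote 12 sends the reader to Section 5.3.3, which requires the full panel at each point. The row has its own mark for every visit, and the liver monitoring described in Section 2.3 and the planned laboratory analyses make no sense without serial labs. A scheduled lab at a new visit also need not count as a repeat of the previous visit's lab; on that reading the footnote concerns only redundant draws around one visit. The lab count then measures a reading that sites are not expected to adopt.

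Much of this stands. The intent is clear from the rest of the protocol, and the count is a ceiling and not a forecast. But the other sections reveal the intent without rewording the rule, and confining the footnote to redundant draws still leaves its condition backwards: it would then forbid a redundant draw only when the earlier one was old.

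A second reply is that changing the instruction from a prohibition to a permission goes beyond restoring a missing word. That is true of the wording, but permission is how footnote 15 frames its own exemption, and it leaves the investigator free to redraw when clinically indicated, as Section 5.3.3 expects.

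**Conclusion.** The point holds and is minor. Footnote 12 is complete, current text whose condition is inverted, and it contradicts the row it annotates and Sections 5.3.3 and 6.2.2. Taken literally it reaches C1V2 and every later Visit 1 lab: 4 to 5 per patient if time on treatment matches the published median PFS range (an assumption), and 6 over six full courses. This is an upper bound. The expected loss is likely small, because sites will probably read the footnote as intended, and the documents give no basis for estimating it. The finding bears on safety monitoring only; the primary and key secondary analyses, the sample size and the futility rule do not depend on it.

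**What to change.** Keep the reference to Section 5.3.3 in footnote 12 and replace the second clause with: *but need not be redone when results no older than 48 hours are available*. This restores agreement with the row and with Sections 5.3.3 and 6.2.2, and it gives sites the practical exemption, for example for screening labs drawn the day before C1V1 or an EOT visit just after a scheduled one. The cost is one footnote, by site clarification letter or in the next amendment. The visit schedule, sample size and analyses do not change.
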